5.1.3 Blood Glucose

24 Hour Average Blood Glucose and other glycemic variability variables (such as MAGE, time in range, etc.) will be computed from BGM data using BD proprietary *extractGlucoseVariabilityFeatures()* and *summarizeGlycemicVariability()* functions with following arguments and associated computation per subject for different time ranges (e.g. day, study period, ...).

For BGM data, at least 10 days data for each period are needed for each time period for the analysis. The time window for baseline is defined as the first 14 days of the study. The time window for 3 month is defined as the last 14 days of the third month. The time window for end of study is defined as the last 14 days of the sixth month. The start and end of time window may be manually adjusted based on the actual visit time.

5.1.4 Quality of Life assessments (EQ-5D)

A summary score of the EQ-5D questionnaire will be calculated as in the EQ-5D-3L user guide provided by EuroQol using the proper value set.

5.2 Analysis Methods

5.2.1 Descriptive Statistics

Summary statistics will be provided for all study endpoints. For categorical data, count and percentage will be calculated and 95% confidence interval may be provided. For continuous data, mean with 95% confidence interval, standard deviation, median, and range (minimum - maximum) will be provided.

Graphical summaries may be provided:

- Boxplots showing median, 1st and 3rd quartiles or scatter plots with means and 95% confidence interval for quantitative responses.
- Barplots for discrete responses or discretized continuous responses.

5.2.2 HbA1c

For HbA1c, analysis will be performed using linear mixed effect models to evaluate the effect of personalized teaching of the optimal insulin injection technique in conjunction with the use of disposable BD Micro-Fine Plus 32G pen needles on the response. In the model, subject will be a random effect, time period (baseline, 3 months or end of study) and lipohypertrophy will be fixed effects. Two-way and three-way interactions between fixed effects will be investigated. Only significant interactions will be included in the model. Models will be used to compute estimated mean, difference between baseline and end of study, and corresponding two-sided 95% CI for responses of interest.

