10.1. Projected sample size

Based on data observed in internal studies with similar designs, assuming an HbA1c decrease of 0.4% between baseline and 6 months and a standard deviation of paired differences of 1.2%, a sample size of 73 subjects would be needed to demonstrate statistical significance using a one sample t-test with a power of 80% and alpha equal to 0.05.

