2.3 Sample Size

Based on data observed in internal studies with similar designs, assuming an HbA1c decrease of 0.4% between baseline and 6 months and a standard deviation of paired differences of 1.2%, a sample size of 73 subjects would be needed to demonstrate statistical significance using a one sample t-test with a power

of 80% and alpha equal to 0.05. With a 20% buffer, the sample size needed is 90.

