2.5 Endpoints

2.5.1 Primary Endpoints

Reduction in glycated hemoglobin (HbA1c in %) after 6 months follow up in patients with Type 1 or Type 2 diabetes.

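### The primary HbA1c model names subject as its only random effect over three visits, so the standard error of the month 6 change depends on an unstated equal-variance, equal-correlation assumption

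*SAP*

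**What the plan says.** The primary endpoint in SAP 2.5.1 is "Reduction in glycated hemoglobin (HbA1c in %) after 6 months follow up". SAP 5.2.2 analyses it with a linear mixed model in which "subject will be a random effect, time period (baseline, 3 months or end of study) and lipohypertrophy will be fixed effects". The model is to supply the "difference between baseline and end of study, and corresponding two-sided 95% CI for responses of interest". Neither document names a random slope, a residual correlation structure, visit-specific variances, robust standard errors or a degrees-of-freedom method for this model.

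The sample size has a different basis. SAP 2.3 works from "assuming an HbA1c decrease of 0.4% between baseline and 6 months" and "a standard deviation of paired differences of 1.2" percentage points. Protocol 10.1 concludes that "a sample size of 73 subjects would be needed to demonstrate statistical significance using a one sample t-test with a power of 80" percent.

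SAP 5.2.9 plans a review of residual plots, with transformation if assumptions fail, and sets significance at p below 0.05. Protocol 10.2 allows transformation, fixed-effect models and non-parametric tests as fallbacks.

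**The concern.** A model whose only random effect is a subject intercept, with independent residuals, assumes compound symmetry: the same variance at every visit and the same correlation for every pair of visits. With complete data the estimated month 6 change is still the simple mean change. Its standard error, however, comes from one residual variance pooled over the 0-3, 3-6 and 0-6 month differences.

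If HbA1c values six months apart agree less well than values three months apart, the 0-6 month difference is the most variable of the three. Averaging it with the two shorter intervals then understates its variance.

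What is at stake is the 95% CI and p-value of the only primary endpoint. The paired t-test used for sizing needs no such assumption, so the planned analysis can report more precision than the variance on which the trial was sized.

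**Working it through.** **Inputs from the documents.** Decrease 0.4; SD of the 0-6 month paired differences 1.2; alpha 0.05; power 80%; n = 73 evaluable (SAP 2.3, Protocol 10.1). Three visits, with subject as the only random effect (SAP 5.2.2).

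**Inputs assumed.** Correlations between visits and the ratios of the visit SDs. The documents give neither.

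**1. The plan's own figure.** The two-sided normal approximation gives (1.960 + 0.842)² × 1.2² / 0.4² = 70.6, so 71. The exact one-sample t-test gives n = 73 with power 80.2% (n = 72 gives 79.7%). The stated 73 reproduces. The standard error behind it is 1.2/√73 = 0.140, and the 95% half-width is 1.993 × 0.140 = 0.280.

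**2. What the random-intercept model uses.** Let V03, V36 and V06 be the variances of the within-patient differences between visits. With complete data:

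- true variance of the mean 0-6 month change: V06 / n
- variance the model reports: (V03 + V36 + V06) / (3n)
- SE ratio (model/true) = √[mean(V03, V36, V06) / V06]
- with equal variances this is √[(1 − mean correlation) / (1 − correlation 0-6)]

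**3. Fading correlation, equal variances.** V06 is held at 1.2² and n at 73. Worked example for 0.75/0.75/0.65: the mean correlation is 2.15/3 = 0.717, so the ratio is √(0.283/0.350) = 0.900. Type I error is from 40,000 simulated trials per case. The half-width is 1.977 × ratio × 0.140, with 144 degrees of freedom.

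| Correlation 0-3 / 3-6 / 0-6 | SE ratio | Type I error | 95% half-width |
|---|---|---|---|
| 0.75 / 0.75 / 0.65 | 0.900 | 7.6% | 0.250 |
| 0.7 / 0.7 / 0.5 | 0.856 | 9.2% | 0.238 |
| 0.8 / 0.8 / 0.6 | 0.816 | 10.8% | 0.227 |
| equal, 0.7 | 1.000 | 4.9% | 0.278 |

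The paired t-test stayed at about 5% in every case, with half-width 0.280.

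**4. Unequal variances.** Type I error here is 2[1 − Φ(1.96 × ratio)].

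- Baseline SD 0.8 of the later visits, correlations 0.7/0.7/0.5: V03 = 0.52, V36 = 0.60, V06 = 0.84; ratio √(0.653/0.84) = 0.88; type I error 8.4%.
- Month 3 SD 1.3 times the others, correlations 0.7/0.7/0.49: V03 = V36 = 0.87, V06 = 1.02; ratio √(0.92/1.02) = 0.95; type I error 6.3%.
- Month 3 SD 1.5 times the others, same correlations: V03 = V36 = 1.15, V06 = 1.02; ratio √(1.107/1.02) = 1.04; type I error 4.1%. The interval is slightly too wide.

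**5. Dropout and lipohypertrophy in the model.** Mixed-model fits with 90 enrolled, 17 lost before month 6 and lipohypertrophy as a fixed effect gave SE ratios of 0.88, 0.84 and 0.81. The adjacent-visit correlations were 0.5, 0.7 and 0.8, each squared for 0-6 months, with 400 runs per case. The pattern does not depend on complete data.

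**The case against.** **The SAP does not say random intercept or compound symmetry.** That is true. It says only that subject is a random effect, and the package list in SAP 3.1 contains no mixed-model package from which a default could be read. A reader might infer that the SAP knowingly fixes a wrong structure; the text does not go that far. But an intercept with independent residuals is the plain reading. If the sponsor means something else, the structure is unspecified and could be chosen after the data are seen.

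**Fading correlation is not documented, and alone it does not settle the direction.** This stands too. Neither document reports a between-visit correlation, and step 4 shows that a much more variable month 3 reverses the error. A reader might infer that the interval is certain to be too narrow, or that the stated 5% level is certain to be missed. The documents support neither: under equal variances and correlations the model is exact.

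**A paired interval may already be planned.** SAP 5.2.1 promises means with 95% CIs for every endpoint, and the primary endpoint is the reduction itself, so the paired interval could appear there. It would be descriptive, though, and SAP 5.2.2 still assigns the inference to the model. Residual plots, transformation and the non-parametric fallback do not target between-visit covariance.

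**The practical effect is modest.** The estimate is unchanged with complete data, and SAP 2.6 sets no acceptance criteria. At the planned effect of 0.4 both analyses are significant: 0.4/0.140 = 2.85 for the paired test, and 0.4/(0.856 × 0.140) = 3.33 for the model with correlations 0.7/0.7/0.5. In that case the two disagree only for estimates between 0.238 and 0.280, which has a probability of about 7% at a true decrease of 0.4. This limits the severity. It does not make an interval with uncertain coverage a sound primary result.

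**Conclusion.** The point holds conditionally. As written, the primary analysis takes its standard error from an average over three visit pairs, while the contrast of interest and the sample size concern one pair. With similar variances and correlations between 0.75/0.75/0.65 and 0.8/0.8/0.6, the standard error is about 10% to 18% too small and the type I error is about 8% to 11% against a nominal 5%. These figures rest on assumed correlations, on the plain reading of SAP 5.2.2 and on n = 73. The algebra is firm. Whether this trial's interval would be wrong, and by how much, cannot be known from the documents. Since the planned method is valid only under an assumption that the plan neither states nor checks, the SAP should be changed.

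**What to change.** In SAP 5.2.2:

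- Fit HbA1c at the three visits with an unstructured within-subject covariance (visit-specific variances and correlations).
- Use Satterthwaite or Kenward-Roger degrees of freedom.
- Take the month 6 minus baseline contrast and its two-sided 95% CI from that model.
- Report the paired t-interval for the same contrast as a check. It uses the same variance as the sample size calculation.

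The cost is a few words in the SAP and a small change in code. An unstructured covariance for three visits has six parameters (three variances and three correlations) against two under the random intercept, and 73 to 90 patients support that. Data collection and sample size do not change. If compound symmetry does hold, almost nothing is lost: at n = 73 the half-width is 0.280 instead of 0.278.

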10.2. Statistical analysis plan

For descriptive statistics and conclusive statistics, R 3.4.4 or more recent version and Rstudio will be used. The HbA1c and insulin total daily dose will be analyzed using linear models with mixed effects (with transformation or without it, whenever necessary) where

lipohypertrophy will be a fixed effect. Analyses will be done overall and per lipohypertrophy sub-group (with or without LH) whenever the sub-group effect is significant.. Generalized linear models with mixed effects will include logistic models for binomial responses or Poisson models for count responses.

Fixed effect models can be used when models with mixed effects cannot be employed. The effect of different covariates will be studied (including, but not limited to these), such as site, age, BMI, gender and diabetes type, as well as their interaction. The threshold to keep covariates in a model will be $p < 0.05$.

Non-parametric tests will be used if basic assumptions do not hold for the models.

McNemar's test will be used, when necessary, for contingency tables.

Statistical methods will be detailed in a Statistical Analysis Plan. Additional analyses may be performed and will be defined in the Statistical Analysis Plan.

11. Data management

All documents containing personal information of the study participants must be stored at the trial conduct site.

The data collected during the course of the study will be entered in the eCRF. The study participants will be identified by the study participant code which is generated by the eCRF. Patient confidentiality will be maintained throughout the study, including the publication of the study results. The principal investigator or sub-investigator will review and sign each form (eCRF, AE), the system will record the date when it was signed. The investigator's signature is the confirmation that clinical and laboratory data entered in the form are complete, accurate and veracious.

The data obtained and entered in the eCRF are the property of Becton, Dickinson and Company.

The study data, copies of the study materials and the medical documents will be provided to the Ethics Committee of the research center, the authorized bodies for internal audit should it be conducted, and on the audit demand. All data obtained in the course of the study will be stored confidentially for at least 3 years after the end of this trial.

12. Appendices to the clinical trial protocol

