2.1 Study Design

A total of 90 patients will be enrolled. Each center will be offered to supply a sufficient number of patients as study subjects (up to 15 patients). Approximately half of these patients will be with lipohypertrophy (LH), and half will be without. Ideally, each center should recruit half of their patients with and half of their patients without LH. The Sponsor will monitor if the overall balance of 50%/50% is maintained and will advise study centers accordingly. The main goal is to have an equal distribution across the study, not necessarily per site, however, each study center should have at least a distribution of 1/3 versus 2/3 in each group. The optimal injection technique and choice of needle length is based on the Russian Procedural Guidelines on injection techniques and infusions used in the treatment of diabetes mellitus. These Guidelines, in turn, are based on recently published international guidelines by the Forum for Injection Technique Therapy Expert Recommendations (FITTER).

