5.2.9 General Considerations

- Missing Insulin or Glycemic data might be imputed, as described in section 5.2.10.
- Imputation might be used during questionnaire analysis if questionnaire pre-process tools contain an imputation routine.
- p-values less than 0.05 will be considered statistically significant. Multiple comparisons adjustments will be made when adequate.
- For each model above, in case the model fails to converge for discrete responses, the random subject effect may be dropped from the model and the average difference between time periods may be calculated across all subjects.
- Initially, two-way interaction will be included into the model. However, if the interaction is not significant (p-value ≥ 0.05), it will be removed from the final model.
- Main effect and interaction plots may be used to graphically show significant effects for each model.
- Residual plots for each model will be drawn and reviewed to ensure there are no systematic patterns. Transformation of response and/or explanatory variables will be investigated whenever modelling assumptions are not satisfied.

- For analysis on discrete responses, a modeling approach will be attempted first and in cases where there are insufficient occurrences for model convergence or a stable model, difference in proportions between categories will be provided and non-parametric testing may be used if modeling assumptions, with or without data transformation, are not satisfied.

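### Lipohypertrophy-specific HbA1c changes depend on a significance test that true differences below about 0.5 points would usually fail, although lipohypertrophy is a planned 50/50 enrolment quota

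*SAP*

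**What the plan says.** SAP 5.2.2 fits a linear mixed model for HbA1c with subject as a random effect, and with time period (three levels) and LH as fixed effects. Interactions are investigated, and then "Only significant interactions will be included in the model". The model yields the baseline to end-of-study difference with "corresponding two-sided 95% CI for responses of interest". SAP 5.2.3 (total daily dose, TDD) and 5.2.4 (blood glucose) carry the same rule. SAP 5.2.9 sets the threshold: "if the interaction is not significant (p-value ≥ 0.05), it will be removed from the final model".

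Protocol 10.2 adds a reporting condition: "Analyses will be done overall and per lipohypertrophy sub-group (with or without LH) whenever the sub-group effect is significant". The protocol synopsis says the same.

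LH is part of the design. SAP 2.1 states: "Approximately half of these patients will be with lipohypertrophy (LH), and half will be without". Under Protocol 7.1 the sponsor monitors that balance and sets a minimum split of one third to two thirds at each center.

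No section promises LH-specific HbA1c changes regardless of the p-value. The descriptive statistics in SAP 5.2.1 are not said to be split by LH.

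**The concern.** A trial that recruits by LH status invites the question of how much HbA1c changed in patients with LH and in patients without. Protocol 7.7 itself anticipates that patients who stop injecting into LH areas may come to need less insulin. Under the plan, the answer appears only if an interaction test reaches p<0.05, and the sample size was not set for that test.

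Such a gate has two effects. A moderate real difference usually fails the test, the term is removed, and the final model then imposes the same change in both groups. When the test is passed, the estimate has been selected for being large, so on average it overstates the difference.

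Three details are also open. The term sub-group effect in Protocol 10.2 could mean the LH main effect, a difference in HbA1c level that says nothing about a difference in change. SAP 5.2.2 does not say which LH assessment enters the model, although LH is examined at Visits 1, 3 and 5 (Protocol Table 2) and is itself an outcome in SAP 5.2.7. If the interaction is kept, the SAP does not say how the overall change is averaged over the LH groups.

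**Working it through.** **Inputs from the documents.** Assumed overall decrease 0.4 points, SD of paired differences 1.2, 73 evaluable and 90 enrolled (Protocol 7.1 and 10.1, SAP 2.3); design test "one sample t-test with a power of 80% and alpha equal to 0.05"; LH split about 50:50 (SAP 2.1); "p-values less than 0.05 will be considered statistically significant" (SAP 5.2.9).

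**Assumptions.** The true LH difference in month 6 change is not given, so 0.2 to 0.8 points is used. The SD of 1.2 is applied within each LH group. The groups are 36 and 37 of 73, or 45 and 45 of 90.

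**Step 1: the plan's own figure.** In a two-sided one-sample t-test with noncentrality (0.4/1.2)√n, power is 79.7% at n = 72 and 80.2% at n = 73. The stated 73 is reproduced. It covers the overall change only.

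**Step 2: standard error of the LH difference in change.** SE = 1.2 × √(1/n1 + 1/n2).
- 36 vs 37: 1.2 × √(1/36 + 1/37) = 0.281
- 45 vs 45: 1.2 × √(2/45) = 0.253

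**Step 3: smallest observed difference that reaches p<0.05.**
- 71 df: 1.994 × 0.281 = 0.56
- 88 df: 1.987 × 0.253 = 0.50

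Power is 50% at almost the same true values, 0.56 and 0.50.

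**Step 4: probability of passing the gate, and exaggeration when passed.** Power uses the noncentral t with noncentrality difference/SE. Exaggeration is the mean absolute estimate among significant results divided by the true difference (simulated).

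| True LH difference | Power, 36 vs 37 | Power, 45 vs 45 | Exaggeration, 36 vs 37 | Exaggeration, 45 vs 45 |
|---|---|---|---|---|
| 0.2 | 11% | 12% | 3.4 | 3.1 |
| 0.4 | 29% | 35% | 1.8 | 1.7 |
| 0.6 | 56% | 65% | 1.3 | 1.2 |
| 0.8 | 80% | 88% | 1.1 | 1.1 |

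The 3.4 becomes 3.5 if the SE is treated as known instead of estimated.

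**Step 5: sensitivity at a true difference of 0.4.**
- Two-df period-by-LH test over three time points, with residual variance 1.2²/2 = 0.72: 22% to 29% (n = 73) and 27% to 35% (n = 90), depending on the month 3 pattern.
- Split of 1/3 to 2/3: 26% (24 vs 49) and 31% (30 vs 60).
- SD 1.0 or 1.4 instead of 1.2, at n = 73: 39% or 23%.

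**Step 6: effect on the overall change.** With complete data, 36 vs 37 patients and a true difference of 0.4, the pooled and equally weighted changes differ by 0.4 × (0.5 − 36/73) = 0.003 points. Dropping the interaction adds about 0.4² × 0.25 = 0.04 to a change variance of 1.44. The interval then widens by √(1.48/1.44) = 1.014, or about 1%.

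**Step 7: precision if both groups are always reported.** The 95% half-width at n = 73 is about 2 × 1.2/√36 = 0.40 per group and 0.56 for the difference. At 45 vs 45 it is about 0.36 and 0.50. For 80% power at a difference of 0.4, the number per group is 2 × 1.2² × (1.96 + 0.84)²/0.4² ≈ 142, or 284 in total.

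**The case against.** The strongest reply is that the trial does not set out to compare LH groups. Neither the objectives nor the SAP endpoints name an LH difference, and avoiding LH tissue is one of four technique components in a hypothesis about all patients. Low power for an interaction that was never powered is normal. This stands: it rules out calling the trial underpowered for a stated aim, and it is why the remedy is estimation and not a larger sample. It does not justify letting a p-value decide whether the two quota groups are described.

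A reader might infer that the primary result is compromised because the final model is chosen from the data. The documents do not support that. Protocol 10.2 provides the overall analysis in either case, and Step 6 shows a shift of about 0.003 points and a CI change of about 1%.

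A reader might also infer that any LH difference would be hidden. That is too broad. If the benefit were confined to one group (0.8 versus 0, averaging 0.4), the gate would be passed 80% to 88% of the time, with only 7% to 12% exaggeration.

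Two further points hold in part. The SAP governs what stays in the final model and does not forbid reporting the tested interaction; the one explicit reporting trigger is in Protocol 10.2. And because Protocol 10.2 defers detail to the SAP, whose rule concerns interactions, the main-effect reading of sub-group effect is mainly a matter of protocol wording.

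**Conclusion.** The point holds as one about LH-specific reporting. True differences below about 0.56 points (n = 73) or 0.50 points (n = 90) would be dropped more often than not and overstated when shown. A difference of 0.4, as large as the whole assumed overall effect, would fail the gate 65% to 71% of the time and be overstated about 1.7 to 1.8-fold when it passed.

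This rests on the plan's SD of 1.2 applied within each LH group, a near-even split, and an assumed range of differences. The documents give no LH difference; their 0.4 is the overall change. No size was worked out for TDD or blood glucose, where the same rule applies.

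It would be tempting to add that a 50/50 mix makes the overall change artificial. The documents give no LH prevalence, so one can say only that the mix is set by quota.

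**What to change.** 1. In SAP 5.2.2 to 5.2.4, keep period-by-LH in the HbA1c, TDD and blood glucose models whatever its p-value, and exempt this term from the removal rule in SAP 5.2.9.
2. Define LH as status at Visit 1, because LH is also a post-baseline outcome.
3. Always report the month 6 change with 95% CI in patients with LH, in patients without LH, and the difference between them. Label these as estimation and not as a powered test.
4. Keep the overall change as the primary HbA1c result, averaged over the LH groups with weights fixed in the SAP before the data are analysed.
5. Remove the significance trigger for LH analyses from Protocol 10.2 and the synopsis, including the ambiguous term sub-group effect.

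The cost is wording, two model degrees of freedom and about three extra table rows per analysis. TDD is analysed separately from diary and CRF (SAP 5.1.1), so there are four analyses and about twelve rows. The sub-group intervals will be wide, as Step 7 shows for HbA1c. No new data or patients are needed.
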